13.2 Phase II Single-Arm Toxicity Monitoring and Efficacy Trial

Phase II single-arm trial will be conducted to assess the overall response rate (ORR) for patients treated at the MTD. Only patients with abnormal HER-family and c-Met signaling activity based on CELsignia MP Test results will be included in the efficacy analysis. The target ORR will be 25%, with unacceptable ORR as 5%.

We will monitor the ORR using the Bayesian optimal phase 2 (BOP2) design (Zhou, Lee and Yuan, 2017)²⁸. The assessment window for ORR monitoring is 4 cycles. Specifically, let n

denote the interim sample size and N denote the maximum sample size. Let p_{eff} denote the ORR and define the null hypothesis $H_0: p_{eff} \leq 0.05$, under which the treatment is deemed as unacceptable. We will stop enrolling patients and claim that the treatment is unacceptable if

$$Pr(p_{eff} > 0.05 | data) < \lambda \left(\frac{n}{N} \right)^\alpha,$$

where $\lambda=0.84$ and $\alpha=0.86$ are design parameters optimized to maximize power under the alternative hypothesis $H_1: p_{eff} = 0.25$, (i.e., the probability of correctly claiming that the treatment is acceptable under H_1), while controlling the type I error rate (i.e., the probability of incorrectly claiming that the treatment is acceptable under H_0) at 0.05. This optimization is performed assuming a vague prior Beta(0.05,0.95) for p_{eff} . The above decision rule leads to the following stopping boundaries and yields a statistical power of 0.95 under H_1 :

Table 20. Optimized Stopping Boundaries

# patients treated	Stop if # responses <=
15	0
29	3

Based on Table 20, we perform the interim analysis when the number of enrolled patients reaches 15. When the total number of patients reaches the maximum sample size of 29, we reject the null hypothesis and conclude that the treatment is acceptable if the number of responses is greater than 3; otherwise we conclude that the treatment is unacceptable. The go/no-go criteria in Table 20 are non-binding and final decision will be based on the total evidence of efficacy.

Below are the operating characteristics of the design based on 10000 simulations using the BOP2 web application, which is available at <http://www.trialdesign.org>.

Table 21. Operating Characteristics

Response rate	Early stopping (%)	Claim promising (%)	Sample size
0.05	46.3	5.3	22.5
0.15	8.7	63.9	27.8
0.25	1.3	94.8	28.8
0.35	0.2	99.6	29.0

Toxicity monitoring

We will monitor the Grade 3+ toxicity rate over 2 treatment cycles (28 days/cycle). Patients treated on Phase 1b at the MTD will be included for Phase II toxicity monitoring. Assuming 9

patients from phase 1b, the total sample size for toxicity monitoring will be $29+9=38$. Formally, we will stop accrual if at any time: $\text{Pr}(\text{Grade 3+ toxicity} > 0.20 \mid \text{Data}) > 0.90$, with a prior beta(0.1, 0.4). Stopping boundaries given an initial cohort of 6 followed by cohorts of 6 patients and with a total of up to 38 patients are:

Table 22. Safety Stopping Boundaries for Phase II

Number of Total Patients (Cohorts of 6)	Discontinuation of arm if Grade 3+ toxicity \geq
6	3
12	5
18	7
24	8
30	10
38	12

Below shows the operating characteristics of toxicity monitoring rule:

Table 23. Operating Characteristics of Toxicity Monitoring

True Toxicity	Probability of Early Stop	Avg. N Patients*
.1	.02	37.4
.2	.19	33.0
.3	.57	23.9
.4	.89	14.7
.5	.99	9.7

*include assumed 9 patients in phase I

Considering that patients with ER+ breast cancer will receive additional treatment with an aromatase inhibitor, in addition to the above overall toxicity monitoring rule, we will perform additional safety monitoring for the first 3 and 6 patients of ER+ breast cancer patients using the BON de-escalation boundaries provided in Table 18. That is, ≥ 2 out of 3 or 6 ER+ breast cancer patients experience a DLT after receiving additional treatment with an aromatase inhibitor, the enrollment of ER+ breast cancer will be paused and dose reduction may be performed for ER+ breast cancer patients based on the totality of the data.

Analyses of secondary outcomes will occur after all subjects have completed the study or completed at least 3 treatment cycles, each spanning 28 days, for a total of 84 days. A 95% level of confidence will be assumed.

Incidence of adverse events will be summarized by CTCAE level as counts with percentages.

Clinical benefit rate (CBR) is defined as the rate of patients who achieved complete response, partial response and stable disease for ≥ 24 weeks. The CBR proportion will be reported together with 95% confidence interval.

Duration of response (DOR) is defined as the period from the date of the first occurrence of a CR or PR until the first date that progressive disease or death is documented. Progression-Free survival (PFS) is defined as the time from treatment onset to either disease progression or death from any cause. 2 year overall survival (OS) is defined as the time from treatment onset to death over 2 years. For events that have not occurred by the time of data analysis, times will be censored at the last contact at which the patient was known to be progression-free for DOR and PFS, or the last time the patient was known to be alive for OS. DOR, PFS and OS will be summarized by the Kaplan-Meier method, including estimates of median and mean survival along with 95% CI.

IND Office Safety and Efficacy Stopping Rule Monitoring:

The Investigator is responsible for completing toxicity summary reports and submitting them to the IND office Medical Monitor for review. These should be submitted as follows:

- **Phase 1b Dose-Finding:**

- A toxicity summary will be submitted after the first 3 evaluable patients complete 2 cycles (56 days) of study treatment, and every 3 evaluable patients thereafter, prior to changing dose levels or moving to the study Phase II portion. IND Sponsor approval will be obtained after each submission, prior to enrolling additional subjects.

- **Phase II – Toxicity Monitoring:**

A toxicity summary will be submitted after every 6 evaluable subjects complete 2 cycles (56 days) of study treatment until enrollment is complete. Patients treated at the MTD in the phase I portion will be included for phase II toxicity monitoring evaluation.

- An additional toxicity summary will be submitted for the subjects with ER+ breast cancer treated at the MTD with AI therapy, after the first 3, and first 6 evaluable patients with ER+ breast cancer treated at the MTD with AI therapy complete 2 cycles (56 days) of study treatment. This toxicity summary may include patients with ER+/HER2- breast cancer treated at the MTD in phase 1b and phase 2. If ≥ 2 out of 3 or 6 patients with ER+ breast cancer experience a DLT at the MTD, the MTD may be decreased to a lower dose level and used for patients with ER+ HER2 negative breast cancer in phase 2.

- **Phase II – Efficacy Monitoring:**

An efficacy summary will be submitted after 15 evaluable subjects complete 4 cycles of study treatment. Final efficacy summary will be submitted when enrollment is complete. Only patients with abnormal HER-family and c-Met

signaling activity based on CELsignia MP Test results will be included in the efficacy analysis.

A copy of each safety summary report should be placed in the Investigator's Regulatory Binder under "Protocol Summary".

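### Section 13.2 says type I error is controlled at 0.05, but the Table 20 boundaries give 0.053, as Table 21 itself shows (minor)

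*Combined protocol and SAP*

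**What the plan says.** Section 13.2 sets the hypotheses for overall response rate: "The target ORR will be 25%, with unacceptable ORR as 5"%. The two BOP2 tuning parameters are described as "design parameters optimized to maximize power under the alternative hypothesis" of a 25% rate, "while controlling the type I error rate", with the limit given as 0.05. On power, the section says: "The above decision rule leads to the following stopping boundaries and yields a statistical power of 0.95 under" the alternative.

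Table 20 gives the resulting rule: stop if there are 0 responses in 15 patients, and claim the treatment acceptable only with more than 3 responses in 29. Table 21 gives operating characteristics from 10,000 simulations. At a response rate of 0.05 it shows 46.3% early stopping, 5.3% in the Claim promising column and a mean sample size of 22.5. At 0.25 it shows 1.3%, 94.8% and 28.8.

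Between the two tables the section adds: "The go/no-go criteria in Table 20 are non-binding and final decision will be based on the total evidence of efficacy". It does not comment on the difference between 0.05 and 5.3%, and it gives no operating characteristics for a trial in which a boundary is set aside.

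**The concern.** The text defines type I error as the chance of wrongly claiming acceptability when the true response rate is at most 5%. The Claim promising entry in the 0.05 row of Table 21 is that same quantity, taken at the edge of the null hypothesis, where it is largest. One section thus gives a limit of 0.05 and a value above it. Controlling a rate at 0.05 is normally read as an upper bound.

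The non-binding sentence adds a second gap. Table 21 assumes the interim stop is obeyed, as its early-stopping and mean sample-size columns show. Continuing after 0 of 15 gives the trial another route to a claim, so the tabulated figure does not cover a path that the plan permits.

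What is at stake is the error rate attached to the primary phase II decision. A later report that quotes the text and not the table would give a rate slightly lower than the design has.

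**Working it through.** **Inputs, all from Section 13.2.** Null rate 0.05; alternative 0.25; prior Beta(0.05, 0.95); lambda 0.84 and alpha 0.86; interim at 15, final at 29; Table 20 boundaries 0 and 3.

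**Step 1: do the stated parameters give Table 20?** Compare the posterior probability that the response rate exceeds 0.05 with the cutoff 0.84 × (n/29)^0.86.

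- n = 15: the cutoff is 0.476. The posterior is 0.016 with 0 responses (stop) and 0.487 with 1 (continue).
- n = 29: the cutoff is 0.84. The posterior is 0.834 with 3 responses (not acceptable) and 0.949 with 4 (acceptable).

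Table 20 is reproduced.

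**Step 2: does Table 20 give Table 21?** Let X1 ~ Binomial(15, p) be the responses at the interim and X2 ~ Binomial(14, p) those among the remaining patients.

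P(claim) = sum over x = 1 to 15 of P(X1 = x) × P(X2 ≥ 4 − x)

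| True rate | Early stop, exact (Table 21) | Claim, exact (Table 21) | Mean N, exact (Table 21) |
|---|---|---|---|
| 0.05 | 46.3% (46.3) | 5.28% (5.3) | 22.5 (22.5) |
| 0.15 | 8.7% (8.7) | 63.85% (63.9) | 27.8 (27.8) |
| 0.25 | 1.3% (1.3) | 94.81% (94.8) | 28.8 (28.8) |
| 0.35 | 0.2% (0.2) | 99.61% (99.6) | 29.0 (29.0) |

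Table 21 is reproduced to within 0.1 point in every row.

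**Step 3: type I error with the interim stop followed.** At p = 0.05:

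| X1 | P(X1) | Needed from the last 14 | Probability | Product |
|---|---|---|---|---|
| 0 | 0.4633 | trial stopped | – | 0 |
| 1 | 0.3658 | at least 3 | 0.0301 | 0.0110 |
| 2 | 0.1348 | at least 2 | 0.1530 | 0.0206 |
| 3 | 0.0307 | at least 1 | 0.5123 | 0.0157 |
| 4 or more | 0.0055 | none | 1 | 0.0055 |

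The products sum to 0.0528. The excess over 0.05 is 0.0028, or 0.28 percentage points. Power at 0.25 by the same formula is 0.9481.

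**Step 4: only the interim stop overridden, final rule kept.** The row X1 = 0 now contributes 0.4633 × P(X2 ≥ 4) = 0.4633 × 0.0042 = 0.0019. The total is P(X ≥ 4; 29, 0.05) = 0.0548, an excess of 0.48 points. Power is P(X ≥ 4; 29, 0.25) = 0.9545 (0.954 to three decimals).

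**Step 5: final rule overridden as well.** A decision on total evidence has no specified rejection region, so no type I error can be computed.

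**Step 6: could 5.3% be simulation noise around 5.0%?** The standard error with 10,000 runs is √(0.053 × 0.947 / 10,000) = 0.0022, so 5.3% alone would not exclude a true 5.0%. The exact value of 0.0528 does: the excess belongs to the boundaries.

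**The case against.** The strongest reply is that nothing is hidden. Table 21 prints 5.3% and 94.8% in the same section, so a careful reader sees the achieved rates. That stands. A reader might infer that the plan conceals or substantially misstates its error rate; the documents do not support this, because the correct figure is in the plan's own table.

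A second reply is rounding. To two decimals 0.053 is 0.05, just as the stated power of 0.95 is 0.948 in full. This may well explain the wording. It does not make the statement true as an upper limit.

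A third is that the sentence describes the constraint used to choose the parameters, while Table 21 reports what was achieved. This stands in part. It is a reason not to overwrite 0.05 with 0.053, which would misdescribe the optimisation. But the achieved rule exceeds the constraint, and the text does not say so.

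A fourth is that discreteness forces the excess. It does not: with the same cutoffs and 28 patients, type I error is 0.0476 (0.0491 with the interim ignored) and power 0.939 (0.945). That shows the limit was attainable; it is not a reason to change the design here.

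Finally, the size is trivial for a single-arm study that Section 2.1 presents as a search for a clinical signal, with confirmatory studies to follow. That also stands, and it is why the point is minor.

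**Conclusion.** Minor, but wrong as written. Section 13.2 claims control at 0.05; its boundaries give 0.0528. That is about 3 additional false claims per 1,000 trials of a treatment with a true 5% response rate (0.0028 × 1,000), or about 5 (0.0048 × 1,000) if the interim stop alone is overridden. The boundaries, Table 21 and the rounded power of 0.95 all check out; only the statement about type I error fails.

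Two stronger readings should be resisted. The mismatch does not show that the boundaries or the sample size are faulty. Nor is 0.055 the error rate for overriding Table 20 in general: it holds only if the final rule of more than 3 of 29 is kept, and the non-binding sentence covers that rule as well.

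The figures assume independent patients with a common response rate, response known for exactly 15 patients at the interim, and 29 at the end.

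**What to change.** Keep 0.05 in Section 13.2, described as the nominal target of the optimisation. Beside it, or as a note under Table 21, add wording to this effect:

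> For the rule in Table 20 the achieved type I error is 0.053 and power 0.948 when the interim stop is followed. If only the interim stop is overridden and the final rule of more than 3 responses in 29 is kept, they are 0.055 and 0.954. If the final rule is also set aside, no type I error can be stated.

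Boundaries, sample size, analysis and conduct are unchanged. The cost is a short note and a stated error rate slightly less favourable than 0.05.

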Study Design	
This is an open-label, phase Ib/II study of neratinib plus Capmatinib in patients with metastatic breast cancer and patients with metastatic IBC.
 
Phase 1b – Dose Escalation of Neratinib with Capmatinib
 
This phase of the study will employ the Bayesian optimal interval (BOIN) design with the 3+3 design run-in, to find the MTD. The BOIN design is implemented in a simple way similar to the traditional 3+3 design, but is more flexible and possesses superior operating characteristics that are comparable to those of the more complex model-based designs, such as the continual reassessment method (CRM). The maximum sample size for dose escalation is 18. Patients are treated in cohorts of 3, beginning with Neratinib PO dose level 1 (120 mg, Dose 1-7, 160 mg, through end of treatment, see Table 2) in combination with Capmatinib PO level 1 (400 mg, see Table 3), with a maximum of 12 patients per dose. The target toxicity rate for the maximum tolerable dose (MTD) is 25%.
 
Phase II
 
Phase II will be a prospective, open label, interventional study for patients with previously treated HER2-negative metastatic breast cancer or metastatic inflammatory breast cancer. Subjects receive Capmatinib in combination with Neratinib (including an AI for patients with ER+/HER2- breast cancer). The MTD determined during Phase 1b will be used.
 
This portion of the trial will be conducted to assess the overall response rate (ORR) for patients treated at the MTD. The target ORR will be 25%, with unacceptable ORR as 5%. We assess the ORR using the Bayesian optimal phase 2 (BOP2) design (Zhou, Lee and Yuan, 2017).
 
Up to an additional 29 evaluable subjects with measurable disease will be enrolled. An interim analysis will be performed when the number of enrolled patients reaches 15.

Number of Patients	Total: 47 patients
Number of Sites	1 site
Study Population	
Phase 1b: previously treated HER2-positive and HER2-negative, ER-positive and ER-negative metastatic and inflammatory breast cancer patients.
 
Phase II: previously treated HER2-negative, ER-positive and ER-negative metastatic and inflammatory breast cancer patients with abnormal HER-family and c-Met signaling tumors. The CELsignia Multi-Pathway (CELsignia MP) Test will characterize the subjects' HER-family and c-Met-driven signaling pathways as either hyperactive or normally active.

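### The interim ORR trigger is stated in two incompatible ways, and the final ORR decision does not require a completed 4-cycle response window; counting at enrollment would put power below the stated 0.95

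*Combined protocol and SAP*

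**What the plan says.** Three places tie the interim look to enrollment. Section 13.2 says "Based on Table 20, we perform the interim analysis when the number of enrolled patients reaches 15", and the Synopsis and Section 4.2 both say "An interim analysis will be performed when the number of enrolled patients reaches 15". The IND Office monitoring text at the end of Section 13.2 sets a different milestone: "An efficacy summary will be submitted after 15 evaluable subjects complete 4 cycles of study treatment".

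For the final look, Section 13.2 says "When the total number of patients reaches the maximum sample size of 29, we reject the null hypothesis" if there are more than 3 responses. The IND Office text adds "Final efficacy summary will be submitted when enrollment is complete". Neither sentence carries a follow-up condition.

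Section 13.2 also says "The assessment window for ORR monitoring is 4 cycles". Cycles are 28 days (Section 7.2), so the window is 112 days. Imaging is every 2 cycles (Section 7.10), so responses are first seen at about day 56 or day 112. Table 20 counts "patients treated", while the IND Office text counts evaluable subjects. The rule is qualified: "The go/no-go criteria in Table 20 are non-binding and final decision will be based on the total evidence of efficacy".

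**The concern.** The 0/15 and 3/29 boundaries can be applied to mature or immature data depending on which sentence is followed. The two interim triggers lie at least 112 days apart. For the final decision, no sentence requires the last patients to complete the window.

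Other sections do not supply a cut-off. Section 5.1 defines ORR by best response with no time point. Section 7.8 ties the end of study to survival or safety data. Nothing says how a patient with a pending assessment is counted.

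If pending patients count as non-responders, an active regimen is more likely to be declared unacceptable than Table 21 shows, and the published operating characteristics would not describe the look that was taken.

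**Working it through.** **Inputs from the plan.** Null ORR 0.05 and target 0.25; stop at 0 responses in 15; claim activity if more than 3 in 29; prior Beta(0.05, 0.95), λ = 0.84, α = 0.86 (Section 13.2). Window 112 days, scans about every 56 days. Planned Phase II accrual 0-2 per month per site (Section 4.4), with one site (Synopsis).

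**Step 1: reproduce the boundaries.** The cutoff is 0.84 × (n/29)^0.86.
- n = 15: cutoff 0.476. The posterior probability that ORR exceeds 0.05 is 0.016 with 0 responses and 0.487 with 1, so stop at 0.
- n = 29: cutoff 0.84. The posterior probability is 0.834 with 3 responses and 0.949 with 4, so at least 4 are needed.

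**Step 2: reproduce Table 21.** With all outcomes known, P(claim) = Σ over x = 1..15 of P(X₁ = x) × P(X₂ > 3 − x), where X₁ ~ Bin(15, p) and X₂ ~ Bin(14, p). This gives 0.0528, 0.6385, 0.9481 and 0.9961 at p = 0.05, 0.15, 0.25 and 0.35. Early stopping at p = 0.25 is 0.75^15 = 0.0134. All agree with Table 21, so that table assumes complete outcomes at both looks.

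**Step 3: patients still pending.** Assumptions that the documents do not fix: even accrual (30.44 days/rate between patients) and pending patients counted as non-responders. The spacing is 60.9, 30.4 or 15.2 days.

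| Rate per month | ≥56 / ≥112 days at 15th enrollment | ≥56 / ≥112 days at 29th enrollment |
|---|---|---|
| 0.5 | 14 / 13 | 28 / 27 |
| 1 | 13 / 11 | 27 / 25 |
| 2 | 11 / 7 | 25 / 21 |

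So on the day patient 29 enrolls, 2, 4 or 8 patients lack the full window, and 1, 2 or 4 have not reached a first scheduled scan.

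**Step 4: power with pending outcomes.** Let m₁ and m₂ be the numbers with known outcomes at the two looks. Then P(claim) = Σ over x = 1..m₁ of P(Bin(m₁, p) = x) × P(Bin(m₂ − m₁, p) > 3 − x), and the false interim stop is 0.75^m₁. Each range runs from all responses first seen at day 112 to all first seen at day 56, with p = 0.25.

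| Rate per month | Mature interim, final at enrollment: power | Both at enrollment: power | Both at enrollment: false interim stop |
|---|---|---|---|
| 0.5 | 0.929-0.939 | 0.922-0.936 | 1.8-2.4% |
| 1 | 0.901-0.929 | 0.884-0.922 | 2.4-4.2% |
| 2 | 0.808-0.901 | 0.744-0.884 | 4.2-13.3% |

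Examples at 2/month: (m₁, m₂) = (15, 21) gives 0.808, and (7, 21) gives 0.744 with a false stop of 0.75^7 = 0.133. With a mature interim the false stop stays at 1.3%.

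**Step 5: later counts and type I error.** With a mature interim and the final count 84 days after last enrollment, power is 0.939-0.948 at 0.5 and 1/month and 0.929-0.948 at 2/month. At 112 days it is 0.948 at every rate. Across the early-count cases, type I error is 0.016-0.048, below the 0.053 of the fully observed design.

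**The case against.** The strongest reply is that the plan intends mature data. The 4-cycle window is stated for ORR monitoring generally, and the IND Office text applies it at the interim. Reaching 15 or 29 can be read as naming a denominator rather than a data-cut date. Completed enrollment can be read as a reporting milestone. The Synopsis and Section 4.2 speak of 29 evaluable subjects, so a patient without a scan might simply not yet be counted. Section 13.2 also holds the secondary analyses until all subjects have completed the study or at least 3 cycles (84 days), which suggests that nothing is analyzed on the day of last enrollment.

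Much of this stands for the interim: a mature look was probably meant, so the figures with both looks at enrollment are the less likely case. It does not settle the final look. The IND Office text makes the interim wait but sets no such condition on the final summary. The 84-day condition covers secondary outcomes only and is shorter than the 112-day window. Evaluability for response is not defined, so it cannot be relied on to delay the count.

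It is also fair that the power loss depends on several assumptions together. With a mature interim, 1 patient/month and half of responses seen at day 56, power is 0.915, about 3 points below 0.948. The non-binding clause softens the consequence, but it does not say which data enter the count.

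**Conclusion.** The concern holds. The interim trigger is contradictory, and the final ORR decision lacks a maturity condition; both are certain from the text. The loss of power is conditional on counting at enrollment, on treating pending patients as non-responders, and on accrual and time to response, which the documents do not fix.

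Under those assumptions the loss ranges from about 1 point (0.5/month, mature interim, responses seen at day 56) to about 20 points (2/month, both looks at enrollment, responses seen only at day 112). The lowest values need accrual at the top of the planned range and no response visible at the first scan. Irregular accrual would make the loss somewhat larger: simulated power with both looks at enrollment under Poisson accrual at 2/month is 0.67-0.85. The harm is a higher chance of rejecting an active regimen, not a false claim of activity. It should be corrected, but it does not undermine the design itself.

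**What to change.** State one trigger in the Synopsis, Section 4.2, Section 13.2 and the IND Office text:
- **Interim:** when each of the first 15 CELsignia-abnormal patients has completed the 4-cycle window, or has progressed, died or stopped earlier.
- **Final ORR decision and final efficacy summary:** the same condition for all 29.
- **Early leavers:** those without a post-baseline assessment count as non-responders, consistent with the fixed denominators of 15 and 29 behind Tables 20 and 21. Reconcile this with the evaluable-subject wording in the Synopsis, Section 4.2 and the IND Office text.
- **Accrual:** say whether enrollment pauses while the interim outcomes mature.

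The boundaries, N = 29 and the stated power need no change. The cost is a final decision about 112 days after last enrollment. If accrual continues during the interim wait, 112/30.44 = 3.68 months adds about 2, 4 or 7 patients at 0.5, 1 or 2/month. At 2/month the expected sample size under the null would then be about 0.463 × 22 + 0.537 × 29 ≈ 26, rather than the 22.5 in Table 21, and that entry should be updated if accrual is not held.

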4.2 Phase II

Phase II will be a prospective, open label, interventional study with previously treated HER2-negative metastatic breast cancer and metastatic inflammatory breast cancer patients. Subjects receive capmatinib in combination with neratinib. The MTD determined during Phase 1b will be used.

This portion of the trial will be conducted to assess the overall response rate (ORR) for patients treated at the MTD. The target ORR will be 25%, with unacceptable ORR as 5%. We will assess the ORR using the Bayesian optimal phase 2 (BOP2) design (Zhou, Lee and Yuan, 2017).

Up to an additional 29 evaluable subjects with measurable disease will be enrolled. An interim analysis will be performed when the number of enrolled patients reaches 15.

The study Phase II portion safety and efficacy data will be monitored by the IND Office.

Treatment response will be evaluated per RECIST tumor response through QIAC.

4.3. Subject Population to be included:

In the Phase 1b portion of the study, previously treated HER2-positive and HER2-negative, HR-positive and HR-negative metastatic and inflammatory breast cancer patients will be enrolled.

In the Phase II portion of the study, previously treated HER2-negative, HR-positive and HR-negative metastatic and inflammatory breast cancer patients with abnormal HER-family and c-Met signaling tumors will be enrolled. The CELsignia Multi-Pathway (CELsignia MP) Test will characterize the subjects' HER-family and c-Met-driven signaling pathways as either hyperactive or normally active.

4.4 Number of Subjects per Study Group:

Phase Ib

This portion of the study will enroll a maximum of 18 patients in the dose-finding trial including the possibility of adding up to 6 additional ER+ HER2 negative patients in a safety assessment of aromatase inhibitor treatment. The statistical considerations used to derive this sample size are presented in Section 13.1.

Phase II

This portion of the study will enroll a maximum of 29 patients. The statistical considerations used to derive this sample size are presented in Section 13.2.

Total accrual of this study will be up to 47 patients. We plan the enrollment for Phase Ib dose escalation to be 1-3 per 2 months since the DLT observation period is 2 months; and for Phase II to be 0-2 per month for each open site.

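### The final success bar of more than 3 of 29 responses is declared non-binding along with the interim look, so the stated type I error and power hold only if that bar is followed, which the plan does not guarantee

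*Combined protocol and SAP*

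**What the plan says.** Three statements in Section 13.2 bear on the point.

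- **Error control.** Before Table 20, the design parameters are said to maximize power "while controlling the type I error rate (i.e., the probability of incorrectly claiming that the treatment is acceptable under H_0) at 0.05". The resulting boundaries are said to give power 0.95 at an ORR of 25%.
- **Final rule.** After Table 20, at 29 patients, "we reject the null hypothesis and conclude that the treatment is acceptable if the number of responses is greater than 3"; with 3 or fewer, the treatment is to be concluded unacceptable.
- **Status of the rule.** The sentence straight after that reads "The go/no-go criteria in Table 20 are non-binding and final decision will be based on the total evidence of efficacy".

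Table 20 has two rows: at 15 patients, stop with 0 responses; at 29 patients, fail with 3 or fewer. The plan does not define what counts as the total evidence. It also does not say that the test of the null hypothesis stays fixed while only a later development decision is flexible.

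**The concern.** A futility look that the team may override is common and does little harm. The final row is different. The plan defines type I error as a false claim that the treatment is acceptable, and the final row decides whether that claim is made. If the claim may also rest on unspecified evidence when 3 or fewer patients respond, the stated error rate no longer describes the decision it was defined for.

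The trial is single-arm, and the secondary and exploratory endpoints in Sections 5.2 and 5.3 carry no success thresholds. No second pre-set criterion would therefore stand in for the response bar. Section 2.1 makes a clear response rate the trigger for confirmatory studies, so the conclusion has consequences.

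**Working it through.** **Inputs, all from Section 13.2.** Null ORR 0.05, target ORR 0.25, interim at 15 (stop at 0 responses), final at 29 (success at 4 or more), prior Beta(0.05, 0.95), and cutoff 0.84 × (n/29)^0.86. Section 4.4 confirms the maximum of 29.

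**Step 1: the boundaries.** Compare the posterior probability that ORR exceeds 0.05 with the cutoff.

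| n | Cutoff | Posterior just below the bar | Posterior just above the bar |
|---|---|---|---|
| 15 | 0.4765 | 0 responses: 0.016 | 1 response: 0.487 |
| 29 | 0.84 | 3 responses: 0.834 | 4 responses: 0.949 |

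Both rows of Table 20 reproduce.

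**Step 2: Table 21.** Let X29 be the responses among 29 patients, X15 those among the first 15 and X14 those among the last 14. For a final bar of b responses with the interim stop kept,

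P(claim) = P(X29 ≥ b) − P(X15 = 0) × P(X14 ≥ b).

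At ORR 0.05 and b = 4:

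- P(X29 ≥ 4) = 1 − (0.2259 + 0.3448 + 0.2541 + 0.1204) = 0.0548
- P(X15 = 0) = 0.95^15 = 0.4633, the 46.3% early stopping in Table 21
- P(X14 ≥ 4) = 0.0042
- P(claim) = 0.0548 − 0.4633 × 0.0042 = 0.0528

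At ORR 0.25 and b = 4: 0.9545 − 0.0134 × 0.4787 = 0.9481.

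These match the 5.3% and 94.8% in Table 21. The rows for 0.15 (63.9%) and 0.35 (99.6%) match as well. The calculation is exact, so the excess of 0.0528 over 0.05 is a property of the rule and not simulation noise.

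**Step 3: which row matters.** Ignoring the interim stop but keeping the final bar moves type I error from 0.0528 to 0.0548 and power from 0.948 to 0.9545. The interim row is not the problem.

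**Step 4: relaxing the final bar.** The plan gives no lower bar, so b = 3 and b = 2 are assumptions. They take every result at that count to be called acceptable. At ORR 0.05:

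| Success claimed with | Interim stop kept | Interim stop ignored |
|---|---|---|
| 4 or more of 29 (the plan's rule) | 5.3% | 5.5% |
| 3 or more of 29 | 16.1% | 17.5% |
| 2 or more of 29 | 35.8% | 42.9% |

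For b = 3 with the interim kept: 0.1751 − 0.4633 × 0.0301 = 0.1612. For b = 2: 0.4292 − 0.4633 × 0.1530 = 0.3583.

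**Step 5: the other direction.** If the wider evidence led to a no-go at exactly 4 responses every time (b = 5, interim kept), type I error would be 1.3% and power 88.1%.

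**The case against.** A reader might infer that the claim of type I error control has no basis. The documents do not support that: the boundaries follow from the stated prior and cutoffs, and every row of Table 21 reproduces.

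A reader might also infer that the plan permits rejecting the null hypothesis with 3 or fewer responses. The text does not say so. The test is stated without qualification, and the next sentence changes vocabulary to go/no-go criteria and a final decision. That could mean a fixed test with a flexible development decision. This reading is possible and perhaps intended, but no section states it. The sentence names Table 20 as a whole, whose final row is the test, so the ambiguity stands.

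The relaxed-bar figures are upper values for assumed bars. A team would not necessarily accept every 3/29 result, and 2/29 is an observed rate of 6.9%, close to the 5% null. They show sensitivity and do not estimate the trial's actual error rate.

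Finally, Section 2.1 describes the trial as seeking a signal, with confirmatory studies to follow, and efficacy summaries go to the IND Office. Both soften the consequence of a false claim, but neither fixes the bar.

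**Conclusion.** The point holds as an inconsistency within Section 13.2 that leaves the stated error rate unassured. The 5.3% and 94.8% apply if the final bar is followed; the plan declares that bar non-binding and does not define the evidence that may override it. One response of leeway, always used, would roughly triple the false-claim rate at ORR 5%, from 5.3% to 16.1% (17.5% with the interim also ignored). Two responses would take it to 35.8% (42.9%). These figures rest on exact binomial calculation and on the assumption that every result at the lower count is accepted. Overrides toward no-go would work the other way. Separately, even with both rows followed, the exact type I error is 0.0528, slightly above the 0.05 that the text says is controlled.

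**What to change.** Amend Section 13.2 in three respects.

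1. Limit the non-binding status to the futility look at 15 patients.
2. State that more than 3 responses in 29 are required to reject the null hypothesis and to conclude that the treatment is acceptable on the primary endpoint. The wider evidence may inform whether to pursue further development, but does not change that conclusion.
3. Replace the stated 0.05 with the exact value: 0.053 if the interim stop is followed, up to 0.055 if it is non-binding.

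The change is a few words, with no effect on sample size or conduct. The sponsor gives up the freedom to call a missed primary endpoint a success, and the reported type I error becomes slightly less favourable. If a fixed test with a flexible development decision was always intended, items 1 and 2 only write that down.
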